2.1. PCSK9 Inhibitors

Two monoclonal antibodies (evolocumab and alirocumab) that inhibit proprotein convertase subtilisin/kexin type 9 (PCSK9) were approved that can reduce low-density lipoprotein cholesterol (LDL-C) concentration beyond statin therapy alone. PCSK9 promotes LDL-receptor degradation, which can lead to increased LDL-C. The PCSK9 inhibitors bind to PCSK9 next to the region that is required for LDL-receptor interaction,

thus more LDL-receptors remain in circulation, which decrease circulating LDL-C. PCSK9 drugs also decrease apolipoprotein B (Apo B).

These drugs were initially approved based on 6-month outcome studies with LDL-C as a surrogate endpoint for longer-term cardiovascular outcomes. While these drugs have a biomarker tied to long-term clinical outcomes, most biologics are not approved based on a surrogate endpoint. However, FDA biosimilars guidance indicates that biomarkers should be tied to the mechanism of action, but not necessarily long-term clinical outcomes. In addition to assessing specific PD biomarkers and their parameters (e.g. area under the effect curve and time of maximal response) at single dose levels, we will also explore applying modeling-based approaches (e.g., Emax, EC50, and slope of concentration-effect relationship) to the PD data.

2.2. Summary

This study will obtain data over a range of doses, including information on the steep part of dose-/exposure-response curve, to inform clinical trial operating characteristics of subsequent PK and PD similarity studies for these drugs. This would be similar to and could substitute for what is suggested as a pilot study in the existing FDA biosimilars guidance. The study will collect data on various PD markers to better understand the dose-response relationship and variability in healthy subjects of traditional PD measurement-based approaches at a single dose (e.g. AUEC and maximal response at a single time point). The study will also evaluate use of model-based approaches for analyzing data from the various dose levels to inform dose selection for similarity studies. In addition, as many biologics from other classes do not have biomarkers associated with the known mechanism-of-action, this study will explore the use of proteomics and small RNA transcriptomics, and the analytical approach needed to identify and characterize circulating biomarkers that could be used for a PD similarity assessment.

3. Study Objectives

3.1. Primary Objective

The primary objective of this study is:

1. To inform clinical trial operating characteristics for future clinical pharmacology PK and PD similarity studies using the different biomarker-based approaches.

3.2. Secondary Objectives

The secondary objectives of this study are:

- 1. To determine the values and variability of PK and PD parameters at four dose levels (i.e., low, intermediate low, intermediate high, and high doses).
- 2. Explore PK and PD relationships using appropriate models

3.3. Exploratory Objective

The exploratory objective of this study is:

- 1. To evaluate the utility of circulating proteins and small RNAs as potential PD biomarkers.
- 2. To inform on the analytical approach and experimental design needed for identifying exploratory proteomic- and RNA-based PD biomarkers in plasma

4. Study Endpoints

4.1. Primary Endpoint

The primary endpoint of this study is:

1. The values and variability of standard PD metrics (AUEC and maximal difference at a single time-point) for LDL-C at low, intermediate low, intermediate high, and high doses of evolocumab and alirocumab.

4.2. Secondary Endpoints

The secondary endpoints of this study are:

- 1. The values and variability of standard PD metrics (AUEC and maximal difference at a single time-point) for ApoB at low, intermediate low, intermediate high, and high doses of evolocumab and alirocumab.
- 2. The values and variability of pharmacokinetic characteristics (Cmax and AUC of free drug concentration) at low, intermediate low, intermediate high, and high doses of evolocumab and alirocumab.
- 3. Parameters (Emax, and EC50) calculated by the model after combining data from low, intermediate low, intermediate high, and high doses of evolocumab or alirocumab with placebo data.

4.3. Exploratory Endpoints

The exploratory endpoints of this study are:

- 1. Plasma proteomics (differential expression of circulating proteins)
- Plasma small RNA transcriptomics (differential expression of circulating small RNAs)
- 3. Differential levels will be evaluated in a systemic approach starting with high doses (discovery) of evolocumab and alirocumab, respectively, then progressing through intermediate high, intermediate low, and low doses (replication phases).

5. Investigational Plan

5.1. Study Design

This is a randomized, placebo-controlled, single-dose, parallel arm study. Healthy subjects will be randomized to four dose groups (low, intermediate low, intermediate high, and high) of each drug (evolocumab or alirocumab) or placebo (See Table 5-1).

Subjects will report to the study site for screening assessments from days -21 to -2 and then will return to the site on day -1 for baseline assessments. Prior to and following study drug or placebo administration on day 1, they will undergo assessments as described in the Schedule of Events (Table 9-1). Subjects will stay in house for the first week and will return to the clinic for study procedures as identified in the Schedule of Events (Table 9-1).

Depending on the treatment arm, subjects will return to the clinic up to 9 times for PK and PD blood draws and additional study procedures as outlined in the Schedule of Events (Table 9-1).

All subjects will be sampled daily for the first week. Subjects in groups A, B, E, and F will follow the schedule of events through day 42. Subjects in groups C and G will follow the schedule of event through day 56. Subjects in groups D, H, and I will follow the schedule of events through day 84. Each treatment group should include equal representation of male and female subjects.

Table 5-1: Study Treatment Groups

Subjects (n)	Treatment Group	Drug
8	A	Evolocumab low (21 mg)
8	В	Evolocumab intermediate low (35 mg)
8	С	Evolocumab intermediate high (70 mg)
8	D	Evolocumab high (140 mg)
8	Е	Alirocumab low (15 mg)
8	F	Alirocumab intermediate low (25 mg)
8	G	Alirocumab intermediate high (50 mg)
8	Н	Alirocumab high (100 mg)
8	I	Placebo

5.1.1 Common Procedures

At the study clinic (Spaulding Clinical Research unit in West Bend, Wisconsin), subjects will be screened for study eligibility from Day -21 to Day -2. On Day -1, subjects will enter the study clinic for check-in procedures the day before study drug administration. During the screening visit, the inclusion and exclusion criteria will be reviewed to ensure the subject is appropriate for the study. The informed consent form will be reviewed with

the subject by a member of the study team and the subject will be encouraged to ask questions to ensure the subject has a good understanding of the study. If the subject is eligible and agrees to participate, the subject will be asked to sign the informed consent form before any study-specific procedure is performed, including randomization.

After the consent process is complete, demographic data, medical history, and concomitant medications (including over-the-counter and complimentary/alternative supplements) will be recorded. A physical examination will be performed by a study team member. Clinical laboratory tests (hematology, serum chemistry, and urinalysis) will be performed. Female subjects must have a negative pregnancy test result. Any values outside the reference range will be evaluated for clinical significance. If a value is determined to be clinically significant or the subject has a positive pregnancy test result, the subject will be instructed to follow-up with his or her personal physician. Screening tests will be performed within 21 days of and no later than 1 day before Day -1.

Screening procedures will be performed by clinic staff, and all screening results will be evaluated by the study clinician/investigator against the inclusion/exclusion criteria to confirm subject eligibility. At check-in, eligibility criteria will be reviewed, any changes in medical history (including concomitant medications) will be documented, vital sign measurements and a 12-lead ECG will be performed, clinical laboratory, drug and alcohol, and pregnancy tests (for females) will be performed, an intravenous (IV) catheter may be inserted into the subject's forearm region for blood collection (if needed), study drug will be administered, and blood samples will be collected per protocol.

The FDA project biostatistician will prepare the randomization schedule, and subjects will be randomly assigned to 1 of 9 treatment groups, described in Table 5-1.

Subjects will enter the study clinic for check-in procedures the day before study drug administration of the first period (Day -1). All study drugs will be administered subcutaneously. On Day 1, subjects will receive their assigned treatment according to the randomization schedule.

5.1.2 Dosing Schedule

- Treatment Group A: Evolocumab 21 mg, SC
- Treatment Group B: Evolocumab 35 mg, SC
- Treatment Group C: Evolocumab 70 mg, SC
- Treatment Group D: Evolocumab 140 mg, SC
- Treatment Group E: Alirocumab 15 mg, SC
- Treatment Group F: Alirocumab 25 mg, SC
- Treatment Group G: Alirocumab 50 mg, SC

• Treatment Group H: Alirocumab 100 mg, SC

• Treatment Group I: Placebo SC

Subjects assigned to treatment groups A, B, E, and F will be discharged from the study on Day 42, subjects assigned to treatment groups C and G will be discharged from the study on Day 56, and subjects in treatment groups D, H, and I will be charged from the study on Day 84. If a subject discontinues from the study prematurely, all procedures scheduled for discharge Day (e.g., Day 42 for treatment groups A, B, E, and F) will be performed. Meal timing and components, activity levels, and general conditions in the study clinic will be as similar as possible on the treatment days.

Safety will be evaluated in terms of AEs, clinical laboratory results (hematology, serum chemistry, and urinalysis), vital sign measurements (blood pressure, heart rate, respiratory rate, and oral body temperature), safety 12-lead ECG results, and physical examination findings (see Table 9-1).

5.1.3 Risk/Benefit

Subjects will be informed that participation in a human PK-PD study like the present one cannot be of benefit to healthy volunteers. Nevertheless, the information from the physical examination, vital sign measurements, and ECG results may be shared with the subject's personal physician if this is the subject's choice. Subjects will be informed that it is also their choice to inform their personal physician that they are participating in this research study.

Subjects will be informed that their contribution to the study is of major importance to agencies like the U.S. FDA for helping this agency better evaluate biomarkers. However, since this is a study involving healthy volunteers, subjects will be informed that they have the alternative not to participate.

Subjects will be informed that they may be exposed to risks associated with the pharmacological properties of the investigational product and the study procedures. The following summary of potential AEs for the study drugs will be provided to and discussed with the subjects:

1. Evolocumab (1)

- Hypersensitivity reactions: Angioedema, rash, and urticaria have occurred.
- Common adverse reactions (> 5% of patients treated with REPATHA and occurring more frequently than placebo in previous clinical trials):
 nasopharyngitis, upper respiratory tract infection, influenza, back pain, and injection site reactions, diabetes mellitus.

2. Alirocumab (2)

- Hypersensitivity reactions (e.g., pruritus, rash, urticaria), including some serious events (e.g., hypersensitivity vasculitis and hypersensitivity reactions requiring hospitalization).
- Commonly occurring adverse reactions (≥5% of patients treated with PRALUENT and occurring more frequently than with placebo in previous clinical trials) are nasopharyngitis, injection site reactions, and influenza.

The study drugs will not be administered to anyone who is pregnant. All women must take a pregnancy test before receiving any study drug in this study. All woman of childbearing potential enrolled on this study will be informed that they must use effective birth control methods (abstinence, intrauterine device, and contraceptive foam and a condom [i.e., double-barrier method]) during treatment. Subjects will be informed that they must notify the investigator if they or their female partners become pregnant during the course of the study.

Subjects will be informed that insertion of an IV catheter may be required for blood sample collection and, during insertion of the catheter, soreness, bruising, or infection at the insertion site are possible but unlikely. Subjects will also be informed that dizziness and lightheadedness may occur during direct venipuncture, insertion of the IV catheter, or during blood collection.

Subjects will be informed that they may eat only meals and snacks that are provided during periods of their stay in the study clinic, and that they must consume all of each meal that is served at a reasonable pace (within 25 minutes).

Subjects will be informed that blood samples will be collected for genomic testing to explore how a person's genes or genome may affect the way the body and drug interact.

Subjects will be informed that the confidentiality of their data will be respected at all times according to state law, and the study personnel handling their study data are bound by confidentiality agreements.

Subjects will be informed that extra precautions will be put in place that will limit the risk of COVID-19. Precautions will be documented in a COVID-19 risk management plan. Currently, this includes phone screening to prevent symptomatic participants from entering the clinic; triage of all potential study subjects entering the building at screening and check-in for potential contacts with COVID-19, signs and symptoms, temperature monitoring and potential serology screening for severe acute respiratory syndrome corona virus 2 (SARS CoV-2); SARS CoV-2 molecular testing just prior to or at check-in for admission to the study floor; all study participants and staff wearing masks except when in a private room or for a limited time for a study procedure (e.g. study drug administration); staff wearing personal protective equipment, social distancing during screening and in-house stays including 1 subject per room for overnight stays; extra hand sanitation stations with hand washing and sanitation policies per CDC recommendations;

closing common areas and serving food at subjects' room resulting in subjects spending most of their time in their rooms with the exception of specified times for walking in the halls; daily temperature screening; and separate staff for confined vs. not-confined participants whenever possible. Designated isolation rooms will be set up to segregate any participant(s) that develop any symptoms of concern while housed in the unit and COVID-19 testing will be done when deemed necessary by the Investigator. When subjects return to the site for follow-up, outpatient visits that require entering the building will also have COVID-19 triage. When outpatient visits only require a blood draw, this may be performed in a covered area outside the building. Subjects will be informed that despite the extra precautions there is still a risk of them contracting COVID-19. Any changes to the COVID-19 precautions (e.g. due to updated CDC recommendations or new testing becoming available) will be documented in the COVID-19 risk mitigation plan.

Subjects will be informed that the study drug and all tests, procedures, and visits required by the study are provided at no cost to them. If subjects become ill or physically injured because of participation in this study, they will be informed that costs of treatment will not be covered by the sponsor.

If a subject becomes pregnant, she will be informed that neither Spaulding Clinical Research nor the sponsor will be responsible for the cost of any obstetric or related care, or for the child's care.

5.2. Selection of Study Population

Subjects will be screened, and the data collected will be reviewed by the principal investigator. Only those subjects who meet all of the eligibility criteria will be enrolled. Approximately 72 healthy subjects are planned for enrollment. Up to 14 subjects may be qualified as replacements as described in Section 5.5.2. Thus, a maximum of 86 subjects will be exposed to study drugs and procedures during the study. Every effort will be made to maintain an approximate 50:50 male to female sex distribution.

5.2.1 Inclusion Criteria

Subjects who meet all of the following inclusion criteria will be eligible to participate in the study:

- 1. Subject signs an IRB approved written informed consent and privacy language as per national regulations (e.g., Health Insurance Portability and Accountability Act authorization) before any study related procedures are performed.
- 2. Subject is a healthy man or woman, 18 to 55 years of age, inclusive, who has a body mass index of 18.5 to 32.0 kg/m², inclusive, at Screening.
- 3. Subject has a LDL-C level >=100 and <=190 mg/dL inclusive, at Screening.

- 4. Subject has normal medical history findings, clinical laboratory results, vital sign measurements, 12 lead electrocardiogram (ECG) results, and physical examination findings at Screening or, if abnormal, the abnormality is not considered clinically significant (as determined and documented by the investigator or designee).
- 5. Subject must have a negative test result for alcohol and drugs of abuse at screening and Check-in (Day -1).
- 6. Female subjects must be of non-childbearing potential or, if they are of childbearing potential, they must: 1) have been strictly abstinent for 1 month before Check in (Day -1) and agree to remain strictly abstinent for the duration of the study and for at least 1 month after the last application of study drug; OR 2) be practicing 2 highly effective methods of birth control (as determined by the investigator or designee; one of the methods must be a barrier technique) from at least 1 month before Check in (Day -1) until at least 1 month after the last application of study drug.
- 7. Male subjects must agree to practice 1 highly effective method of birth control (as determined by the investigator or designee) from at least 1 month before Check in (Day-1) until at least 1 month after the last application of study drug.
- 8. Subject is highly likely (as determined by the investigator) to comply with the protocol defined procedures and to complete the study

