5.2.2 Exclusion Criteria

Subjects who meet any of the following exclusion criteria will not be eligible to participate in the study:

- 1. Subject is taking cholesterol medication (e.g. statins).
- 2. Subject is anemic (i.e., with Hct or Hgb less than the lower limit of normal) or has any chronic condition(s) that may impact blood sample collection.
- 3. Subject has had previous exposure to the biologic Evolocumab or Alirocumab.
- 4. Subject has a history of asthma.
- 5. Subject has a history of anaphylaxis from environmental exposures such as peanuts or bee stings.
- 6. Subject has an allergic history that includes urticaria, angioedema or respiratory coughing or difficulty breathing.
- 7. Subject has a history of severe local reactions or generalized erythema from skin allergen testing.
- 8. Subject has used any prescription or nonprescription drugs (including aspirin or NSAIDs and excluding oral contraceptives and acetaminophen) within 14 days or 5 half-lives (whichever is longer) or complementary and alternative medicines within 28 days before the first dose of study drug.
- 9. Subjects are currently participating in another clinical study of an investigational drug or are have been treated with any investigational drug within 30 days or 5 half-lives (whichever is longer) of the compound.

11

- 10. Subject has used nicotine-containing products (e.g., cigarettes, cigars, chewing tobacco, snuff) within 6 weeks of Screening.
- 11. Subject has consumed alcohol, xanthine-containing products (e.g., tea, coffee, chocolate, cola), caffeine, grapefruit, or grapefruit juice within 48 hours of dosing. Subjects must refrain from ingesting these throughout the study.
- 12. Subject has any underlying disease or surgical or medical condition (e.g., cancer, human immunodeficiency virus [HIV], severe hepatic or renal impairment) that could put the subject at risk or would normally prevent participation in a clinical study. This includes subjects with any underlying medical conditions that put subjects at higher risk for coronavirus disease of 2019 (COVID-19) complications; per current Center for Disease Control and Prevention (CDC) recommendations this includes:
 - People with chronic lung disease or moderate to severe asthma
 - People who have serious heart conditions
 - People who are immunocompromised

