5.5. Criteria for Subject Withdrawal

Subjects may withdraw from the study at any time at their own request, or they may be withdrawn by the investigator without the approval of the subject based on the

investigator's clinical judgment. A subject is not required to provide a written request to withdraw from the study; however, a written request is required if a subject withdraws consent for his or her personal data to be used for study-related purposes.

A subject may be discontinued for any of the following reasons:

- AE: The subject has experienced an AE that, in the opinion of the investigator, requires early termination. The appropriate electronic case report form (eCRF) must be completed for each AE. If a subject is discontinued from the study due to an AE, the investigator is required to follow-up with the subject until the event resolves or becomes stable. If a subject dies during the study, the cause of death must be reported as a serious AE (SAE), with an outcome of death noted in the eCRF.
- Protocol Violation: The subject failed to meet protocol entry criteria or did not adhere to protocol requirements, and continued participation poses an unnecessary risk to the subject's health.
- Withdrawal by Subject: The subject (or other responsible individual [e.g., caregiver]) wishes to withdraw from the study in the absence of a medical need.
 - NOTE: Withdrawal due to an AE should not be recorded in the "voluntary withdrawal" category.
- Study Terminated by Sponsor: The sponsor, IRB, FDA, or other regulatory agency terminates the study.
- Pregnancy: The subject is found to be pregnant.
 - NOTE: If the subject is found to be pregnant, the subject must be withdrawn immediately. The pregnancy will be followed-up to term, and the outcome, including any premature termination will be recorded. All live births must be followed for a minimum of 30 days or until the first well-baby visit.
- Other.

NOTE: This category records withdrawals caused by an accidental or a medical emergency, unblinding, and other rare cases. The specific reason should be recorded in the comment space of the eCRF.

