5.7.4.1.5 Pregnancy

A serum pregnancy test will be performed for female subjects at the time points presented in the Schedules of Events (Table 9-1). If a subject becomes pregnant while on the study, this should be reported immediately to the investigator, the subject will be withdrawn from the study and the medical monitor and the subject will be instructed to follow-up

with his or her personal physician. All pregnancies are to be reported as an AE and followed for outcome.

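### As inclusion 6 is written, women using two birth control methods may stop at about Day 31, before their end of study, while abstinent women are bound throughout; a minor wording gap that is cheap to close

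*Protocol*

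**What the plan says.** Inclusion 6 in Protocol 5.2.1 offers women of childbearing potential two routes. On the first, abstinence, a woman must "agree to remain strictly abstinent for the duration of the study and for at least 1 month after the last application of study drug". On the second she uses two highly effective methods, one of them a barrier, "from at least 1 month before Check in (Day -1) until at least 1 month after the last application of study drug". The synopsis carries the same difference. Inclusion 7 gives men the same end point as the second route.

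Each subject receives one dose, on Day 1. Groups A, B, E and F leave the study on Day 42, and C and G on Day 56. For the others, "Subjects in groups D, H, and I will follow the schedule of events through day 84" (Protocol 5.1).

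Two other places bear on how long a restriction lasts. Section 5.1.3 says women of childbearing potential will be told to use effective methods, ending with "contraceptive foam and a condom [i.e., double-barrier method]) during treatment". Exclusion 11, on alcohol, caffeine and grapefruit, shows how the protocol words a whole-study restriction: "Subjects must refrain from ingesting these throughout the study".

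On pregnancy, Protocol 5.5 says "If the subject is found to be pregnant, the subject must be withdrawn immediately", and 5.7.4.1.5 repeats that "the subject will be withdrawn from the study". SAP 5 leaves subjects who discontinue before their assigned end-of-study day out of the PK and PD parameter summaries.

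**The concern.** The two routes of one criterion end on different days, and no reason is given. With a single Day 1 dose, a minimum tied to the last application expires while every subject is still attending sampling visits. A woman on the second route who stops at that minimum has met the criterion.

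What is at stake is mainly retention. A pregnancy recognised on study forces withdrawal, and SAP 5 then removes that woman from the parameter summaries of an arm of 8. Those summaries carry the primary endpoint, the values and variability of the LDL-C metrics at each dose. A pregnancy on study must also be reported as an adverse event and followed for outcome, whether or not any data are lost.

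**Working it through.** **Inputs.** One dose on Day 1 (synopsis; Protocol 5.1.1). End of study on Day 42, 56 or 84 (5.1, 5.1.2). Lipid sampling days from Day 28 on: 28, 35, 42, 56, 70, 84 (5.7.2.1.1). Eight subjects per arm with about equal numbers of men and women (5.1, 5.2). The length of a month is not defined, so I assume 30 days and show 28 to 31. The plan states no last contraception day, so there is no figure of its own to reproduce.

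**Gap.** Last required day = Day 1 + month length. Gap = end-of-study day − last required day.

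| Month | Last required day | A, B, E, F (Day 42) | C, G (Day 56) | D, H, I (Day 84) |
|---|---|---|---|---|
| 28 days | 29 | 13 | 27 | 55 |
| 30 days | 31 | 11 | 25 | 53 |
| 31 days | 32 | 10 | 24 | 52 |

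**Sampling visits after Day 31.** Days 35 and 42 in A, B, E and F (2 visits); Days 35, 42 and 56 in C and G (3); Days 35, 42, 56, 70 and 84 in D, H and I (5).

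**Women concerned, at most.** 72 × 0.5 = 36 planned: 16 in A/B/E/F, 8 in C/G and 12 in D/H/I. Of these, 4 arms × 4 = 16 are in C, D, G and H, the active arms with a gap of 25 days or more. Section 5.2 allows that "a maximum of 86 subjects will be exposed to study drugs and procedures during the study", which gives 86 × 0.5 = 43. The number who are of childbearing potential and choose the second route is not known.

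**Path to a loss.** A woman must be on the second route, stop at the minimum and conceive. The pregnancy must then be recognised before her end-of-study day. As Table 9-1 reads in the extracted text, pregnancy tests fall only at screening, check-in and end of study, and 5.6.3.2 defers to that table. No scheduled test therefore lies in the gap, and a pregnancy first found at the end-of-study test costs no data.

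**What a withdrawn woman loses.** SAP 5 removes her from the PK and PD parameter summaries. The same section defines the PK and PD populations by receipt of study drug and at least one estimable parameter, and builds the PK/PD population from both. On those definitions she can still enter the exposure-response models. She also remains in the safety population and in the individual plots of SAP 7.3 and 7.4.

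**Scale of one unreplaced loss (8 to 7), for any reason.**
- Mean, 90% CI half-width in SD units: t(0.95, 7)/√8 = 0.670; t(0.95, 6)/√7 = 0.734; ratio 1.096.
- SD, upper/lower ratio of the 90% CI: √[χ²(0.95, 7)/χ²(0.05, 7)] = 2.548; √[χ²(0.95, 6)/χ²(0.05, 6)] = 2.775; ratio 1.089.

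These figures describe any single dropout. They are not an effect of the contraception wording.

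**The case against.** The strongest reply is that 5.1.3 already deals with this. It addresses all women of childbearing potential without separating the two routes. Table 9-1 puts the outpatient visits under its treatment-period heading, and 5.5.2 requires replacements to complete that period. Read this way, contraception runs to the end of study. This reading is reasonable and may be what was intended. But 5.1.3 gives no end day, and with one dose the phrase can also be read narrowly. It describes what women will be told and does not alter the criterion against which they are enrolled. The consent form is not among the documents reviewed and may state a date.

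A second reply is that an end point tied to the last dose, shared with inclusion 7 for men, may be a deliberate choice based on exposure, and that the stated month is only a minimum. That stands as far as it goes: the wording leaves a gap and does not contradict itself. It still does not explain why abstinent women are bound for longer.

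A third reply is that a loss is improbable and replaceable. This also stands. Up to 14 replacements on the same treatment are allowed, although the trigger is left to a separate replacement plan. In A, B, E and F an 11-day gap makes the path remote.

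A reader might go further and infer that a withdrawn woman's data survive only in listings. SAP 5 does not say so: its exclusion covers the parameter summaries only.

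**Conclusion.** The point holds as a minor wording gap. As inclusion 6 is written, a woman on the second route may stop 11, 25 or 53 days before her end of study (10 to 13, 24 to 27 or 52 to 55 for months of 28 to 31 days), while a woman on the first route may not. Section 5.1.3 may be meant to close the gap but does not do so clearly.

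The consequence, if it arises, is withdrawal and absence from the PK and PD parameter summaries. No expected number of losses can be computed, because the documents do not give the number of women on the second route, how many would stop at the minimum, or a conception rate.

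A reader might also infer that one month of contraception is unsafe for a fetus. The documents give no fetal-risk data after Day 31, and no such claim is made. Nor do they support a claim that precision is impaired by about 10%, since that figure belongs to any unreplaced dropout. The point concerns women only: the protocol withdraws a subject who is pregnant, not one whose partner is.

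**What to change.** In the synopsis and in 5.2.1, insert option 1's study-duration clause into option 2, so that the two methods are required from at least 1 month before check-in, for the duration of the study, and for at least 1 month after the dose. In 5.1.3, state that same period in place of the reference to treatment.

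For women who complete, the study-duration clause governs, because the earliest end of study (Day 42) is later than Day 32. The 1-month clause still protects a woman who leaves before about Day 31. The gap in the requirement becomes zero in every arm. Under 5.8.6 subjects and staff learn the end-of-study day at discharge from confinement, so each woman can be given a specific date then without disclosing her arm. No change is proposed for inclusion 7.

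The cost is a wording amendment with no new visits, procedures or analyses. The real burden is up to about 53 more days (52 to 55) of required contraception for women on the second route. This includes women on placebo, who cannot be exempted without unblinding. Because the arm is unknown at consent, the commitment has to be stated as up to Day 84.
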